E. Arm 3 First and Second Salvage AML cohort (AZA + VEN + Nivo) (N=30)

Historical data for salvage patients with azacitidine and venetoclax show an overall response rate (ORR) of 25-50% (DiNardo CD et al, *American journal of hematology* 2018; **93**(3): 401-7; Aldoss I et al, *Haematologica*. 2018 Sep;103(9):e404-e40; Goldberg A et al, *Blood* 2017; **130**(Suppl 1): 1353). It is expected for the current trial that the three-drug combination will improve the ORR by 35% while the toxicity rate is maintained at or below 30%. A sample size of 30 patients ensures that, if the trial is not terminated early, a posterior 90% credible interval for ORR will have width of 0.28 at most, under the assumption of a 60% of ORR rate. The prior probabilities of ORR and toxicity for the experimental regimen are modeled by beta distributions (*Beta* (0.5, 1.5) and *Beta* (0.6, 1.4), respectively). Denoting the historical proportion of overall response rate and toxicity rate by $\{p(\text{ORR},H) = 25\%, p(\text{TOX},H) = 30\%\}$, the following decision criteria will be applied:

- 1) Stop if $\text{Prob}\{p(\text{ORR},H) + \delta_{\text{OR}} > p(\text{ORR},E) \mid \text{data}\} > 0.975$, where $\delta_{\text{OR}} = 0.35$
- 2) Stop if $\text{Prob}\{p(\text{TOX},H) + \delta_{\text{TOX}} < p(\text{TOX},E) \mid \text{data}\} > 0.95$, where $\delta_{\text{TOX}} = 0$

Patients will be monitored in cohorts of 5 according to the following stopping boundaries for overall response and DLT.

| # Patients Evaluated | Stop if this cohort ≤ this # ORR | Stop if ≥ this # toxicities |
|----------------------|-------------------------------------|-------------------------------------|
| 5 | 0-1 | 4-5 |
| 10 | 0-3 | 6-10 |
| 15 | 0-5 | 8-15 |
| 20 | 0-8 | 10-20 |
| 25 | 0-10 | 12-25 |
| 30 | Always stop with this many patients | Always stop with this many patients |

The operating characteristics are summarized in the following table (based on simulations from 10,000 trials).

| True Toxicity Rate | True ORR Rate | PROB(Stop Early) |
|--------------------|---------------|------------------|
| 0.10 | 0.25 | 0.9838 |
| | 0.45 | 0.5615 |
| | 0.60 | 0.1459 |
| | 0.75 | 0.0185 |
| | 0.90 | 0.0011 |
| 0.20 | 0.25 | 0.9840 |
| | 0.45 | 0.5676 |
| | 0.60 | 0.1579 |
| | 0.75 | 0.0322 |
| | 0.90 | 0.0150 |
| 0.30 | 0.25 | 0.9856 |
| | 0.45 | 0.6094 |
| | 0.60 | 0.2393 |
| | 0.75 | 0.1258 |
| | 0.90 | 0.1102 |
| 0.40 | 0.25 | 0.9900 |
| | 0.45 | 0.7297 |
| | 0.60 | 0.4736 |
| | 0.75 | 0.3951 |

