| | 0.90 | 0.3843 |
| 0.50 | 0.25 | 0.9958 |
| | 0.45 | 0.8852 |
| | 0.60 | 0.7764 |
| | 0.75 | 0.7431 |
| | 0.90 | 0.7385 |

F. Arm 3 Frontline Elderly AML cohort (AZA + VEN + Nivo) (N=30)

Historical data for frontline patients treated with venetoclax and hypomethylating agents (DiNardo CD et al, Blood. 2019 Jan 3;133(1):7-17); Pollyea D et al ASH 2018 Oral presentation Abstract 285.: full PowerPoint attached as Appendix) show ORR of 66%. It is expected for the current trial that the

Nivolumab and azacytidine

three-drug combination will improve the ORR by 15-20% while the toxicity rate is maintained at or below 30%. A sample size of 30 patients ensures that, if the trial is not terminated early, a posterior 90% credible interval for ORR will have width of 0.28 at most, under the assumption of a 80% of ORR. The prior probabilities of ORR and toxicity for the experimental regimen are modeled by beta distributions (*Beta* (1.2, 0.8) and *Beta* (0.6, 1.4), respectively. Denoting the historical proportion of overall response rate and toxicity rate by $\{p(\text{ORR}, H) = 0.60, p(\text{TOX}, H) = 0.30\}$, the following decision criteria will be applied:

- 1) Stop if $\text{Prob}\{p(\text{ORR}, H) + \delta_{\text{OR}} > p(\text{ORR}, E) \mid \text{data}\} > 0.95$, where $\delta_{\text{OR}} = 0.2$
- 2) Stop if $\text{Prob}\{p(\text{TOX}, H) + \delta_{\text{TOX}} < p(\text{TOX}, E) \mid \text{data}\} > 0.90$, where $\delta_{\text{TOX}} = 0$

Patients will be monitored in cohorts of 5 according to the following stopping boundaries for overall response and toxicity.

| # Patients Evaluated | Stop this cohort if \leq this # ORR | Stop if \geq this # toxicities |
|----------------------|---------------------------------------|-------------------------------------|
| 5 | 0-2 | 4-5 |
| 10 | 0-5 | 6-10 |
| 15 | 0-9 | 8-15 |
| 20 | 0-12 | 10-20 |
| 25 | 0-16 | 12-25 |
| 30 | Always stop with this many patients | Always stop with this many patients |

The operating characteristics are summarized in the following table (based on simulations from 10,000 trials).

| True Toxicity Rate | True ORR Rate | PROB(Stop Early) |
|--------------------|---------------|------------------|
| 0.10 | 0.60 | 0.7956 |
| | 0.70 | 0.4433 |
| | 0.80 | 0.1221 |
| | 0.85 | 0.0441 |
| | 0.90 | 0.0114 |
| 0.20 | 0.60 | 0.7985 |
| | 0.70 | 0.4511 |
| | 0.80 | 0.1344 |
| | 0.85 | 0.0575 |
| | 0.90 | 0.0252 |
| 0.30 | 0.60 | 0.8180 |
| | 0.70 | 0.5041 |
| | 0.80 | 0.2180 |
| | 0.85 | 0.1485 |

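### Arm 3 frontline cohort: the stated 0.90 toxicity rule and the printed stopping table, which matches a 0.95 rule, give opposite decisions at 9/20 and 11/25

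*Combined protocol and SAP*

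**What the plan says.** Section 11.3 F describes the Arm 3 frontline cohort (N=30). It expects that the "three-drug combination will improve the ORR by 15-20% while the toxicity rate is maintained at or below 30" per cent. The toxicity rate has a Beta(0.6, 1.4) prior and is compared with a fixed historical rate of 0.30 with no added margin. In the document's typesetting, the cut-off in the second decision criterion reads "data}\} > 0.90$, where $\delta_{\text{TOX}} = 0".

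The section continues "Patients will be monitored in cohorts of 5 according to the following stopping boundaries for overall response and toxicity", and the table that follows stops for toxicity at 4–5 of 5, 6–10 of 10, 8–15 of 15, 10–20 of 20 and 12–25 of 25. A table of 25 early-stopping probabilities comes next.

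Section 11.3 E describes the Arm 3 salvage cohort. It uses the same toxicity prior and the same 0.30 reference, but its cut-off reads "data}\} > 0.95$, where $\delta_{\text{TOX}} = 0". Its toxicity column is the same, entry for entry.

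**The concern.** The posterior depends only on the prior, the reference rate and the count, so a cut-off fixes the whole stopping column. Two cohorts that share prior, reference and look times but state different cut-offs should not normally end up with the same column at all five looks. If they do, one column may not follow from its own rule.

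This matters because Section 11.3 F makes both the criterion and the table binding. Section 5.2.2.6 says DLTs are not monitored in the expansion phase and relies instead on a safety check every 5 patients for drug-related grade 3/4 non-haematological events. The table is therefore the working toxicity safeguard for this cohort. If the stated rule is the intended one, the table stops later than it should, and the printed operating characteristics describe a different design.

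**Working it through.** **Inputs (Section 11.3 F unless noted).** Toxicity prior Beta(0.6, 1.4); reference 0.30; margin 0; stated cut-off 0.90; looks at n = 5, 10, 15, 20, 25; maximum 30. Printed response boundaries: stop at 2, 5, 9, 12, 16 or fewer. The response rule has prior Beta(1.2, 0.8), target 0.60 + 0.20 = 0.80 and cut-off 0.95. Section 11.3 E has the same toxicity inputs with cut-off 0.95.

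**Formula.** After x toxicities in n patients the posterior is Beta(0.6 + x, 1.4 + n − x). The boundary is the smallest x for which the posterior probability of a rate above 0.30 exceeds the cut-off.

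**Step 1: does the method reproduce the plan?** The largest response count with posterior probability above 0.95 of a rate below 0.80 is 2, 5, 9, 12, 16. This is exactly the printed response column, so the method is the plan's own.

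**Step 2: toxicity boundaries.** The table shows the printed boundary and the count just below it.

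| n | Printed boundary (posterior) | One count lower (posterior) | Boundary at 0.90 | Boundary at 0.95 |
|---|---|---|---|---|
| 5 | 4 (0.9751) | 3 (0.8745) | 4 | 4 |
| 10 | 6 (0.9625) | 5 (0.8798) | 6 | 6 |
| 15 | 8 (0.9597) | 7 (0.8927) | 8 | 8 |
| 20 | 10 (0.9608) | 9 (0.9059) | 9 | 10 |
| 25 | 12 (0.9634) | 11 (0.9180) | 11 | 12 |

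For example, 9 of 20 gives Beta(9.6, 12.4), with probability 0.9059 above 0.30. 11 of 25 gives Beta(11.6, 15.4), with probability 0.9180. Both exceed 0.90. 8 of 20 (0.8067) and 10 of 25 (0.8380) do not.

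To produce the printed column with this prior, the cut-off must be at least 0.9180 and below 0.9597. The value 0.95 lies in that range and 0.90 does not.

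**Step 3: which rule do the printed operating characteristics describe?** Toxicity and response are taken as independent. Then P(stop early) = 1 − S_T × S_R, where S_T and S_R are the exact binomial probabilities of passing all five toxicity looks and all five response looks. With the printed boundaries, all 25 printed values are reproduced to four decimals.

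Take true ORR 0.80 and true toxicity 0.50. S_T = 1 − 0.7384 = 0.2616 and S_R = 0.8784, so 1 − 0.2616 × 0.8784 = 0.770, against 0.7702 printed. With the 0.90 boundaries, S_T = 1 − 0.8359 = 0.1641 and the result is 0.856 (0.8558 unrounded).

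**Step 4: size of the difference.**

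| True toxicity | Toxicity stop, printed table | Toxicity stop, 0.90 rule | Any early stop at ORR 0.80, printed | Any early stop at ORR 0.80, 0.90 rule |
|---|---|---|---|---|
| 0.10 | 0.0006 | 0.0006 | 0.1221 | 0.1221 |
| 0.20 | 0.0146 | 0.0205 | 0.1344 | 0.1396 |
| 0.30 | 0.1098 | 0.1640 | 0.2180 | 0.2657 |
| 0.40 | 0.3840 | 0.5054 | 0.4589 | 0.5655 |
| 0.50 | 0.7384 | 0.8359 | 0.7702 | 0.8558 |

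**Step 5: could another prior rescue the printed column at 0.90?** Beta(0.5, 1.5) gives 4, 6, 8, 10, 11, which still differs at n = 25. A more informative Beta(3, 7) does give 4, 6, 8, 10, 12, but the documents state no such prior.

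**The case against.** The best defence is that 0.90 is a one-number slip and the table is right. The toxicity column matches 0.95 at every look, the operating characteristics agree with the column, and the other five cohorts in Section 11.3 (A to E) all use 0.95 for toxicity. On that reading no intended protection is lost. This is plausible, and it makes any loss of protection conditional on 0.90 having been meant. It is still an inference, because nothing in the documents settles the question and the text as written says 0.90.

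The scope is also narrow. The first three looks agree, and the decisions conflict only at exactly 9 toxicities in 20 patients or exactly 11 in 25. When the response rule already stops most trials, the overall effect is small: at toxicity 0.50 and ORR 0.60 it is 0.9465 against 0.9664. No overall entry at toxicity 0.20 moves by more than 0.006, and none at 0.10 moves to four decimals.

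Finally, the IND Office reviews a summary after every 5 evaluable patients (end of Section 11.3), and Section 9.2 allows termination at any time for adverse reactions. These provisions limit the harm, but they do not tell a reviewer whether 9 of 20 is a stop.

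**Conclusion.** The concern holds. With the stated prior and reference rate, the 0.90 rule requires stopping at 4, 6, 8, 9 and 11 toxicities, while the table prints 4, 6, 8, 10 and 12. Rule and table give opposite accrual decisions at 9/20 and 11/25.

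Measured against the stated rule, the table lowers the chance of stopping for toxicity by 5.4 percentage points at a true rate of 30%, 12.1 at 40% and 9.8 at 50%. The printed operating characteristics are those of the table and not of the stated rule.

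The boundary result needs only the plan's own prior, reference and cut-off. The stopping probabilities also assume that toxicity and response are independent, an assumption under which the plan's 25 values are reproduced. The documents do not show which version was intended.

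**What to change.** Reconcile the rule, the table and the operating characteristics by amendment before the cohort reaches 20 evaluated patients. There are two ways to do it.

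1. **State the cut-off as 0.95.** One number changes in the second criterion of Section 11.3 F. The table and operating characteristics then stand as printed.
2. **Keep 0.90.** The toxicity cells become 9–20 at n = 20 and 11–25 at n = 25. Of the 25 operating characteristics, 20 change (the toxicity 0.10 row does not), giving:

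| True toxicity | ORR 0.60 | 0.70 | 0.80 | 0.85 | 0.90 |
|---|---|---|---|---|---|
| 0.10 | 0.7956 | 0.4433 | 0.1221 | 0.0441 | 0.0114 |
| 0.20 | 0.7997 | 0.4544 | 0.1396 | 0.0632 | 0.0311 |
| 0.30 | 0.8291 | 0.5344 | 0.2657 | 0.2004 | 0.1731 |
| 0.40 | 0.8989 | 0.7245 | 0.5655 | 0.5269 | 0.5107 |
| 0.50 | 0.9664 | 0.9086 | 0.8558 | 0.8430 | 0.8377 |

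The price of the second option is that stopping for toxicity when the true rate is exactly 30% rises from 11.0% to 16.4%. Neither option changes the sample size or the data collected. The sponsor should say which rule was intended and, if the two Arm 3 cohorts are meant to differ, why.

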1.0 OBJECTIVES

1.1 Primary Objectives

Part a. Lead-in phase:

1. To determine the maximum tolerated dose (MTD) and dose limiting toxicity (DLT) of nivolumab in combination with 5-azacytidine in patients with refractory/ relapsed acute myeloid leukemia (AML).
2. To determine the maximum tolerated dose (MTD) and dose limiting toxicity (DLT) of nivolumab with ipilimumab in combination with 5-azacytidine in patients with refractory/ relapsed acute myeloid leukemia (AML).
3. To determine the maximum tolerated dose (MTD) and dose limiting toxicity (DLT) of nivolumab in combination with 5-azacytidine and venetoclax in patients with refractory/ relapsed AML.

Part b. Phase II

1. To determine the overall response rate (ORR) of nivolumab in combination with 5-azacytidine in patients with refractory/ relapsed AML.
2. To determine the overall response rate (ORR) of nivolumab in combination with 5-azacytidine in older patients (≥ 65 years) with newly diagnosed AML.
3. To determine the overall response rate (ORR) of nivolumab with ipilimumab in combination with 5-azacytidine in patients with refractory/ relapsed AML.
4. To determine the overall response rate (ORR) of nivolumab with ipilimumab in combination with 5-azacytidine in older patients (≥ 65 years) with newly diagnosed AML.
5. To determine the overall response rate (ORR) of nivolumab in combination with 5-azacytidine and venetoclax in patients with refractory/ relapsed AML.
6. To determine the overall response rate (ORR) of nivolumab in combination with 5-azacytidine and venetoclax in older patients (≥ 65 years) with newly diagnosed AML.

1.2 Secondary Objectives:

1. To determine the number of patients who achieve a $> 50\%$ reduction in blasts on therapy with either vidaza+nivolumab, vidaza+nivolumab+ipilimumab or vidaza+venetoclax+nivolumab.
2. To determine the duration of response, event-free survival (EFS), 4- and 8-week mortality, and overall survival (OS) of patients with refractory/ relapsed AML treated with either vidaza+nivolumab, vidaza+nivolumab+ipilimumab or vidaza+venetoclax+nivolumab.
3. To determine the duration of response, event-free survival (EFS), 4- and 8-week mortality, and OS in older patients with newly diagnosed AML treated with either vidaza+nivolumab, vidaza+nivolumab+ipilimumab or vidaza+venetoclax+nivolumab.

1.3 Exploratory Objectives:

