We have thus far treated 70 patients on the vidaza + nivolumab trial for relapsed/refractory AML as of Dec 30 2016 (Daver N, Sharma P et al., American Society of Hematology, 2016 abstract #763). The RP2D of 5-azacytidine and nivolumab was established as 5-azacytidine 75mg/m² days 1-7 and nivolumab 3.0 mg/kg on days 1 and 14 of each cycle in the ongoing clinical trial. 0/6 patients experienced a DLT at this dose during the safety-run-in phase. All subsequent 47 patients have received this RP2D dose of 5-azacytidine and nivolumab. 51 patients have completed at least 3 cycles and are evaluable for response and toxicity. 51 pts with a median age of 69 years (range, 45 – 90), secondary AML (55%), poor risk cytogenetics (47%), median number of prior regimens 2 (range, 1-7) have been enrolled. All 51 pts had baseline next generation sequencing and most frequently detected mutations included *DNMT3A* (n=12), *TP53* (n=11), *TET2* (N=9), *ASXL1* (n=7), and *RAS* (n=7). 35 pts are evaluable for response: 6 (18%) achieved complete remission (CR)/ complete remission with insufficient recovery of counts (CRI) (3 CR, 3 CRI), 5 (15%) had hematologic improvement (HI), 9 (26%) had ≥50% BM blast reduction, 3 pts (9%) had stable disease > 6 months, and 12 (34%) had progression. 16 pts are early for response assessment (<3 courses). The median number of courses to CR/CRI/HI was 3 (1 – 9). The CR/CRI/HI

(n=11) have been durable with no relapses among pts who achieved CR/CRI/HI [CR duration; not reached (NR)]. The 4- and 8-week mortality were 0 and 6%, respectively. The median overall survival for the 35 evaluable pts was 9.3 months (range, 1.8 – 14.3) (Fig 1) and this compares favorably to historical survival with AZA-based salvage protocols in similar pts treated at MDACC.

Grade 3/4 and Grade 2 immune mediated toxicities were observed in 7 (14%) and 6 (12%) pts, respectively. These included 8 episodes of pneumonitis, 2 nephritis, 2 transaminitis, and 1 skin rash. 1 pt died from grade 4 pneumonitis/epiglottitis. In the remaining 12 cases the toxicities responded rapidly to steroids and all 12 pts were successfully rechallenged with nivolumab. Time to onset of toxicities ranged from 4 days to 3.5 months. Four pts were postSCT and one had a grade 3 flare of GVHD of the skin and gut.

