| | 0.90 | 0.1194 |
| 0.40 | 0.60 | 0.8740 |
| | 0.70 | 0.6569 |
| | 0.80 | 0.4589 |
| | 0.85 | 0.4109 |
| | 0.90 | 0.3907 |
| 0.50 | 0.60 | 0.9465 |
| | 0.70 | 0.8543 |
| | 0.80 | 0.7702 |

| Nivolumab and azacytidine | | |
|---------------------------|---------------|------------------|
| True Toxicity Rate | True ORR Rate | PROB(Stop Early) |
| | 0.85 | 0.7498 |
| | 0.90 | 0.7412 |

The Investigator is responsible for completing an efficacy/safety summary report, and submitting it to the IND Office Medical Affairs and Safety Group, for review and approval. This should be submitted as follows:

Lead-in Phase:

Every 6 evaluable patients complete cycle 1 of study therapy before advancing/changing dose levels.

Expansion Phase:

After the first 5 evaluable patients per cohort, complete 3 months of study treatment, and every 5 evaluable patients per cohort, thereafter.

A copy of the cohort summary should be placed in the Investigator's Regulatory Binder under "sponsor correspondence".

Statistical Analysis Plan

All patients who received any dose of the study agent will be included in the analysis for efficacy and safety. Demographic/clinical characteristics (including duration of response) and safety data of the patients will be summarized using descriptive statistics such as mean, standard deviation, median and range. For the primary efficacy analysis, we will estimate the ORR for the combination treatment, along with the 95% confidence interval. Patients who drop out of the study before completing all the cycles will be treated as "failures" for the primary analysis. Overall response rate (ORR) during the study period will also be presented with the 95% confidence interval. The association between ORR and patient's clinical characteristics will be examined by Wilcoxon's rank sum test or Fisher's exact test, as appropriate. Toxicity type, severity and attribution will be summarized for each patient using frequency tables.

The distribution of time-to-event endpoints (DFS and OS) including overall survival and progression free survival will be estimated using the method of Kaplan and Meier.

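### Duration of response and EFS are secondary objectives, but the SAP gives duration of response raw descriptive statistics with no censoring rule and names no analysis of EFS

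*Combined protocol and SAP*

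**What the plan says.** Section 1.2 sets the objective for the salvage cohorts: "To determine the duration of response, event-free survival (EFS), 4- and 8-week mortality, and overall survival (OS) of patients with refractory/ relapsed AML". It repeats it for the frontline cohorts: "To determine the duration of response, event-free survival (EFS), 4- and 8-week mortality, and OS in older patients with newly diagnosed AML". Both apply to all three regimens.

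The Statistical Analysis Plan at the end of Section 11.3 mentions duration of response once, in a parenthesis attached to demographic and clinical characteristics: "including duration of response) and safety data of the patients will be summarized using descriptive statistics such as mean, standard deviation, median and range". The time-to-event sentence reads: "The distribution of time-to-event endpoints (DFS and OS) including overall survival and progression free survival will be estimated", by Kaplan-Meier.

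EFS does not appear anywhere in Section 11. DFS and PFS do, but neither is an objective in Section 1. Section 8.1 defines the response categories. No section defines relapse, or gives a start date, event list or censoring rule for duration of response, EFS, DFS or PFS.

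**The concern.** A response that is still running at data cut-off has a known minimum length but no known end. A mean, standard deviation or simple median of such data needs a decision on what to do with the unfinished responses. The plan makes none. The two obvious choices, counting the time so far as the full duration or dropping the patients still in response, both tend to pull the result down. The SAP uses Kaplan-Meier for other endpoints in the same section, so the right tool is at hand but is not assigned to this endpoint.

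Durability is part of the case for the trial. The Arm 3 rationale in Section 2.6 argues from the limited length of CR/CRi on a hypomethylating agent with venetoclax, and it foresees quick go or no-go comparisons with internal controls. A raw summary from an early cut would be hard to set against a published median.

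For EFS, the report would have no pre-specified analysis to point to. DFS and PFS, undefined here, do not answer an EFS objective unless they are defined to do so.

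**Working it through.** The plan states no precision, event count or target for duration of response or EFS, so there is no figure to reproduce. The check has a textual part and an illustrative calculation.

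**1. Objectives against analyses**

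| Endpoint | Objective in Section 1.2 | Analysis in the SAP |
|---|---|---|
| Duration of response | yes | descriptive statistics, no censoring rule |
| EFS | yes | none named |
| OS | yes | Kaplan-Meier |
| DFS, PFS | no | Kaplan-Meier |

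**2. Will responses be censored?** The Arm 1 update in Section 2.3 C says that the responses of 11 patients "have been durable with no relapses among pts who achieved CR/CRI/HI", and gives CR duration as not reached. Unfinished responses are therefore to be expected, at least at early cuts.

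**3. Size of the bias**

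Inputs:
- True median 11.0 months: the CR/CRi duration that Section 2.3 E reports for frontline venetoclax plus a hypomethylating agent.
- Exponential durations: an assumption.
- Follow-up from response, uniform over *a* to *b* months: an assumption, because Section 9.1.4 keeps patients in follow-up but sets no length.

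Formulas, with ongoing responses counted at their length so far:
- λ = ln 2 / 11.0 = 0.0630, and true mean = 1/λ = 15.9 months.
- Censored fraction q = (e^(−λa) − e^(−λb)) / (λ(b − a)).
- Raw mean = (1 − q)/λ.
- Raw median m solves e^(−λm) × P(follow-up > m) = 0.5.

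Follow-up 0-24 months: q = (1 − 0.220)/1.512 = 0.516. Raw mean = 0.484 × 15.87 = 7.7. At m = 6.23, 0.675 × 0.740 = 0.500, so the raw median is 6.2.

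Follow-up 12-48 months: q = (0.469 − 0.049)/2.268 = 0.185. Raw mean = 0.815 × 15.87 = 12.9. Every follow-up time exceeds 11 months, so P = 1 at m = 11.0 and the raw median is correct.

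| Follow-up (months) | Censored | Raw median (true 11.0) | Raw mean (true 15.9) |
|---|---|---|---|
| 0-12 | 70% | 4.2 | 4.7 |
| 0-24 | 52% | 6.2 | 7.7 |
| 3-24 | 46% | 7.3 | 8.6 |
| 6-36 | 31% | 9.2 | 11.0 |
| 21.7-35.1 | 17% | 11.0 | 13.1 |
| 12-48 | 19% | 11.0 | 12.9 |

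Table 1 in Section 2.3 D shows that both ends are realistic. Median follow-up was 11.8 months for Aza+Ipi+Nivo (a uniform 0-24 range has median 12) and 27.2 months, range 21.7-35.1, for Aza+Nivo.

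In simulation, the Kaplan-Meier median was 10.8, 10.9 and 11.1 months for the 3-24, 6-36 and 12-48 ranges. Dropping patients still in response is worse: the median among relapsed patients only was 5.1, 6.8 and 8.3 months in those three ranges, so it stays low even with long follow-up.

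**4. Salvage patients.** The 11.0-month figure does not apply to them. Section 2.6 gives CR durations under 6 months for relapsed/refractory AML. With a true median of 6 (λ = 0.1155, true mean 8.7) and follow-up 0-24 months, q = (1 − 0.0625)/2.773 = 0.338 and the raw mean is 0.662 × 8.66 = 5.7. The raw median is 4.3, since 0.609 × 0.821 = 0.500. The direction is the same and the gap is smaller.

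**The case against.** Several points against the concern have force.

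- **The plan does not say that censoring will be ignored.** It is silent, its list of statistics is open-ended, and the background already reports a duration as not reached, which is a censoring-aware summary. A reader might infer that durability will be understated. The documents support only that the plan does not commit to a method that would prevent it.
- **The median bias depends on follow-up.** With mature follow-up, and ongoing responses counted at their length so far, it disappears. A reader might infer that a regimen as durable as the reference must look worse than 11.0 months. For the median, the statistic in which that benchmark is expressed, this fails at 12-48 or 21.7-35.1 months.
- **The benchmark is frontline only.** Applying it to all of Arm 3 would be wrong, since the salvage cohort is half of the planned expansion (30 of 60).
- **No relapses is not the same as all 11 still in response.** The update does not exclude death in remission or a lapse in assessment, and it is a 2016 cut of Arm 1.
- **The Kaplan-Meier sentence is garbled.** It reads as loose labelling at least as much as a decision to replace EFS with DFS and PFS.
- **The consequence is limited.** These are secondary endpoints, no test against 11.0 months is planned, and the stopping rules use ORR and toxicity.

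What remains is that the one analysis stated for duration of response gives a mean that is too low whenever responses are ongoing, and that EFS has neither a definition nor a named analysis. Kaplan-Meier has limits too. With an assumed 14 responders, a true median of 11 months and 3-12 months of follow-up, its median was not reached in 55% of simulated samples. That outcome is uninformative but not misleading.

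**Conclusion.** The point holds as a mismatch between Sections 1.2 and 11.3 that should be corrected. The text is clear on both halves: a raw summary without a censoring rule for duration of response, and no definition or analysis of EFS.

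The size is conditional. Under the exponential assumption with a true median of 11.0 months, the raw mean is low in every scenario, from 4.7 to 13.1 months against 15.9. The raw median runs from 4.2 months with 0-12 months of follow-up to the correct 11.0 once all follow-up exceeds the true median. Confidence is high for the gap in the text. The amount of bias cannot be fixed, because the protocol does not set the follow-up. OS is already covered by Kaplan-Meier, and the primary conclusion on ORR does not depend on this point.

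**What to change.** 1. Delete the parenthesis on duration of response from the descriptive sentence.
2. Define duration of response as the time from first response to relapse or death, censored at the last disease assessment. State which response categories count and what constitutes relapse, since Section 8.1 does not.
3. Define EFS: its start date, its component events (including what counts as treatment failure and as relapse), and its censoring rule.
4. Estimate both by Kaplan-Meier, reporting medians with 95% confidence intervals.
5. Keep DFS and PFS only if they are defined; otherwise align the labels in that sentence with the EFS objective.

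The cost is a few SAP sentences, including the event definitions. No new procedures are needed, and the sample size, stopping boundaries and primary ORR analysis do not change.
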